10.6.2.3. Randomized Treatment Discontinuation and Study Withdrawal

Randomized Treatment Discontinuation and Study Withdrawal
Randomized Treatment Discontinuation

 • Randomized Treatment Discontinuation Censored Time (days) = Treatment stop date – Treatment start date +1 
If the treatment stop date = death date for a subject, the subject will be censored and will not be counted as an event for treatment discontinuation summaries that exclude subjects who die while on treatment.

 • Time to Randomized Treatment Discontinuation (days) = Treatment stop date – Treatment start date +1

 • Randomized Treatment Person Years = (Cumulative total of time to randomized treatment discontinuation for subjects who discontinued randomized treatment + Cumulative total of randomized treatment discontinuation censoring time for subjects who did not discontinue randomized treatment) / 365.25

 • Randomized Treatment Discontinuation Incidence Rate (per 100 person years) = $100 * \frac{\text{Number of subjects who discontinued randomized treatment}}{\text{randomized treatment person years}}$
Study Withdrawal

 • Study Censored Time (days) = Study completion date – Randomization date +1

 • Time to Study Withdrawal (days) = Study withdrawal date – Randomization date +1

 • Study Person Years = (Cumulative total time to study withdrawal for subjects withdrawing from the study + Cumulative total of study censoring time for subjects who did not withdraw from study) / 365.25

 • Study Withdrawal Incidence Rate (per 100 person years) = $(100 * \frac{\text{Number of subjects who have withdrawn from study}}{\text{Study Person Years}})$

10.6.2.4. Prior and Concomitant Medications

Prior and Concomitant Medications
Non-randomized ESA use during treatment period

 • Subjects will be considered to have non-randomized ESA use during the treatment period if they have any ESA concomitant medication records with one of the following two reasons for medication: 
 ○ Non-randomized ESA treatment in addition to randomized treatment ○ Non-randomized ESA treatment instead of randomized treatment

CONFIDENTIAL

201410

Prior and Concomitant Medications
Duration of non-randomized ESA use during treatment period

 • If there is only one concomitant medication record of non-randomized ESA use during the treatment period, then: 
 ○ Duration (days) = earliest of (concomitant medication record end date, last non-zero dose date + 1 day) – latest of (concomitant medication start date, treatment start date) + 1 day • If there are multiple concomitant medication records of non-randomized ESA use during the treatment period, then the duration of non-randomized ESA use will add the durations for all records, subtracting any overlapping days that may exist between the multiple records.

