6.6.1. Randomized Treatment Extended Interruption

Every effort must be made to continue randomized treatment and to complete study visits, where able; however, sites should contact their PPD study team member if a subject cannot return to the research site on a temporary basis for any one of the following situations:

- Subjects who are hospitalized for any duration.
- Subjects who cannot return to the site for a period >5 weeks.

In exceptional circumstances, standard of care for anemia management during this time period may be considered based on consultation with the PPD medical monitor. If non-study ESAs are administered, doses should be recorded on the Prior/Concomitant Medications – ESA eCRF page.

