6.2.5. Prior and Concomitant Medications

The number and percentage of subjects reporting the use of each concomitant medication will be summarized by treatment group and overall, anatomical therapeutic chemical (ATC) Level 1, 2, 3, and Ingredient. Summaries of pre-treatment, on-treatment, and post-treatment medication will be provided separately. See Section 10.4.1.5 for a summary of treatment states for concomitant medications.

A listing of on-treatment concomitant medication records will be provided with details of the on-treatment concomitant medication use.

The number and percentage of subjects with any non-randomized ESA use in addition to randomized treatment during the treatment period (see Section 10.6.2) will be provided by treatment group and overall. Similarly, the number and percentage of subjects with any non-randomized ESA used instead of randomized treatment during the treatment period (see Section 10.6.2) will be provided by treatment group and overall. Additionally, the duration of the non-randomized ESA use during the treatment period will be summarized using mean, standard deviation, minimum, P25, median, P75, and maximum by treatment group and overall, as well as by the number and percentage of subjects in the following duration categories: < 5 days, ≥ 5 days - < 14 days, ≥ 14 days - < 28 days, ≥ 28 days.

A listing of subjects who have non-randomized ESA use will be provided with details of the ESA use.

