
Last Non-Zero Dose Date
 
 • Date of last actual dose of randomized study treatment from IP Discontinuation eCRF form. 
 ○ The dose steps used by the dosing algorithm described in the protocol include a dose hold or a zero dose. If subjects are assigned by the algorithm to a zero dose, they do not receive randomized treatment for that period. Hence, it would be possible for a subject to complete the study, while still following the dosing algorithm, but not actually be taking any actual randomized treatment. The last non-zero dose date, then captures the latest date in the study that a subject physically took a dose of randomized treatment. • The eCRF allows for the possibility of partial or missing dates to be recorded for the last actual dose of randomized study treatment on the IP Discontinuation form (i.e., missing day, or day and month, or day and month and year). In such a case, or in case of subjects who have a non-missing treatment start date, but are missing an IP Discontinuation form, the following conventions will be applied in order to impute a last non-zero dose date: 
 ○ Missing day: 
 ▪ The last day of the month will be used, unless the treatment stop date also occurs in the same month; in this case, the treatment stop date will be used. ○ Missing day and month; 
 ▪ ‘31’ will be used for the day and ‘Dec’ will be used for the month, unless the treatment stop date also occurs in the same year; in this case the treatment stop date will be used. ○ Missing day, month, and year: 
 ▪ Treatment stop date will be used only for subjects who have a non-missing treatment start date.

CONFIDENTIAL

201410

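### The duration rule for non-randomized ESA use returns negative days when the ESA starts three or more days after the last physical study dose

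*SAP*

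**What the plan says.** Three parts of SAP 10.6.2.4 (Prior and Concomitant Medications) work together.

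- **Who is a user.** Subjects count as having non-randomized ESA use during the treatment period "if they have any ESA concomitant medication records with one of the following two reasons for medication". One reason is ESA in addition to study drug; the other is "Non-randomized ESA treatment instead of randomized treatment". No date condition is attached.
- **How long.** The duration of a single record runs to the "earliest of (concomitant medication record end date, last non-zero dose date + 1 day"), less the "latest of (concomitant medication start date, treatment start date) + 1 day".
- **Several records.** The calculation "will add the durations for all records, subtracting any overlapping days that may exist between the multiple records".

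The cut-off date is defined in SAP 10.6.1: "The last non-zero dose date, then captures the latest date in the study that a subject physically took a dose of randomized treatment". That section defines the treatment stop date separately, as the latest stop date on the dosing records, and it can fall later.

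SAP 6.2.5 says that "the duration of the non-randomized ESA use during the treatment period will be summarized using mean, standard deviation", together with the minimum, quartiles, maximum and four categories: under 5 days, 5 to under 14, 14 to under 28, and 28 or more. It also reports the number and percentage of users by reason, and a listing.

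Protocol 6.6.1 shows how such records can arise. Local anemia care may be considered during an extended absence, and "If non-study ESAs are administered, doses should be recorded on the Prior/Concomitant Medications" ESA page. Protocol 6.1 allows local care during a supply interruption.

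**The concern.** The user flag and the duration use different time frames. The flag is undated. The duration stops one day after the last physical dose. ESA given in place of study drug may well begin after that date if the subject does not go back to study drug. Such a record is still flagged and still enters the formula, but its start lies after the formula's end point.

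At stake is the description of how long each arm received an outside ESA. The primary analysis keeps hemoglobin values regardless of such use (SAP 7.1.2.4), so a reader of the non-inferiority result may turn to this table to judge exposure to other ESAs. A negative number of days is impossible, and it also pulls down the mean and the lower quantiles.

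**Working it through.** The documents give no numerical result for this derivation, so there is no published figure to reproduce. The check puts dates through the formula. All dates below are assumed examples.

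**Inputs.** L = last non-zero dose date (SAP 10.6.1). T0 = treatment start. S and E = start and end of the ESA record.

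**Formula (SAP 10.6.2.4).** D = min(E, L + 1) - max(S, T0) + 1.

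If E is at or beyond L + 1 and S is at or after T0, this becomes D = (L + 1) - S + 1 = L + 2 - S. The record end has dropped out, so D depends only on the gap between the last dose and the ESA start.

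**A 28-day ESA record at different starts**

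| Record start | D as written (days) |
|---|---|
| Wholly before L | 28 |
| L - 10 | 12 |
| L - 1 | 3 |
| L | 2 |
| L + 1 | 1 |
| L + 2 | 0 |
| L + 3 | -1 |
| L + 7 | -5 |
| L + 14 | -12 |
| L + 28 | -26 |

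The result turns negative at L + 3. A one-day record at L + 21 gives -19, the same as any longer record with that start.

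**Single subjects**

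- Last injection Day 309, ESA Days 337 to 365: 310 - 337 + 1 = -26. The record lasts 365 - 337 + 1 = 29 days.
- The same subject with an earlier 20-day course inside the window: 20 - 26 = -6. The two records together last 20 + 29 = 49 days.
- Last tablet Day 330, ESA Days 340 to 365: 331 - 340 + 1 = -8. The record lasts 365 - 340 + 1 = 26 days.

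**Effect on a mean.** Take ten users: nine with 28 days each, and one with a 14-day record starting at L + 15, for which D = 2 - 15 = -13.

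- As written: (252 - 13)/10 = 23.9 days.
- With a floor at zero: 252/10 = 25.2 days.
- With the 14 days counted: (252 + 14)/10 = 26.6 days.

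**Comparison with the IV iron rule.** SAP 10.6.3.2 faces the same problem for on-treatment IV iron to Week 52. For repeated-dose records it assigns a duration of zero if the record starts after the earlier of treatment stop date + 1 and the Week 52 visit. The ESA rule has no such line, and it ends at the last physical dose instead of the treatment stop date.

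**Effect of the end date.** Suppose the last injection is on day 200, the treatment stop date is day 228, and the ESA record lasts 14 days.

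- Start on day 207: -5 as written; 0 with a floor; 220 - 207 + 1 = 14 with a cut at day 229.
- Start on day 221: -19 as written; 0 with a floor; 229 - 221 + 1 = 9 with a cut at day 229.
- The day-221 record plus a 28-day record inside the window: 28 - 19 = 9 as written; 28 with a floor; 28 + 9 = 37 with the later cut.

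**The case against.** The best defence is that SAP 10.4.1.5 already sets the on-treatment window for concomitant medications other than IV iron, from treatment start to the last non-zero dose date + 1 day. A medication started later is post-treatment only, and a programmer could reasonably drop it here. This stands in part: the cut-off follows the SAP's own convention and is not wrong in itself. It does not cure the problem, because SAP 10.6.2.4 defines use during the treatment period by reason code, so a late record with either code qualifies. The SAP also wrote an explicit zero rule for IV iron and none here.

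A second objection is frequency. Protocol 6.6.1 concerns temporary absences, and ESA followed by a return to study drug lies before L and is computed correctly. The documents do not show how ESA after permanent discontinuation or rescue is coded; if it carries another reason, it never enters this table. This stands: the number affected may be small, and it cannot be derived.

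Third, a negative subject total would show up in the reported minimum, and the listing gives the record details. Also true. But a negative record hidden inside a positive total, as in the 9-day example, would not show in the minimum.

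**Conclusion.** The rule is wrong as written, and minor. A flagged ESA record that starts three or more days after the last physical dose gets a negative duration. That lowers the subject's total and the mean, and can lower the minimum and lower quantiles. A subject with only such records falls in the under-5-days category. The conclusion assumes that the derivation is programmed as stated and that such records carry one of the two reason codes.

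A reader might infer more than this, and the documents do not support it:

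- **That all ESA after the last dose goes negative.** Starts at L + 1 and L + 2 give 1 and 0 days, which is short but not negative. A record straddling L is shortened but stays positive.
- **That the longest courses are made to look the shortest.** For records running past L + 1, duration reflects the gap after the last dose, not course length.
- **That the darbepoetin arm is understated more.** Dosing every 4 weeks makes a longer gap plausible, but darbepoetin is also given every 2 weeks and weekly (Protocol 12.3.1). Equal gaps give equal results in both arms, and the examples above use chosen gaps.
- **That contamination as a whole is under-reported or efficacy is affected.** Counts of users come from reason codes and do not change. The evaluable hemoglobin rule uses ESA record dates (SAP 10.6.3.1). The primary analysis keeps hemoglobin regardless of ESA use (SAP 7.1.2.4). No test uses this duration.

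**What to change.** In SAP 10.6.2.4, define one treatment-period window for this table and apply it to both the user flag and the duration. Set the duration of any record starting after the window to zero, as the IV iron rules do, and exclude that record from the count and the summary. A floor at zero alone is not enough, because it leaves counted users with 0 days.

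The window end is the sponsor's choice. Last non-zero dose date + 1 day keeps the convention in SAP 10.4.1.5. If ESA given in place of study drug after the last physical dose should be described, either end the window at treatment stop date + 1 day, as for IV iron and on-treatment hemoglobin (SAP 10.6.3.2 and 10.4.1.1), or report that use separately as post-treatment. Running the window to Week 52 or study completion would be a preference, since it would count post-treatment days in a display about the treatment period.

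The cost is about one line in the SAP and a matching change in the derivation. No new data are needed. With dates applied to the flag, the number of users may fall for subjects whose only records lie outside the window; a footnote should say so.

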10.6.2.4 Exposure and Compliance

Exposure and Compliance			
Exposure			

 • Exposure (days) = Treatment stop date – treatment start date + 1 day 			
Compliance			

 • Compliance will be calculated based on data recorded in the Study Treatment Details eCRF pages and will only be calculated for subjects with a non-missing treatment start date, and will not be calculated after a subject's treatment stop date, or study conclusion date for subjects who have a non-missing treatment start date and a missing treatment stop date. • A compliance category will be assigned to each randomized treatment exposure record according to the following tables. Exposure records corresponding to periods of dose hold/zero-dose as assigned by the IRT will be categorized in the compliant category and any gaps between exposure records will be categorized in the under compliant category. 
 ○ Daprodustat Doses 			
Under Compliant	Compliant	Over Compliant	
Compliance for the exposure record < 80%	Compliance for the exposure record ≥ 80% and ≤ 120%	Compliance for the exposure record > 120%	
Where compliance for the exposure record is calculated as 100% * $\frac{[\# \text{ dispensed} - (\# \text{ returned} + \# \text{ lost})] / \# \text{ tablets per day}}{(\text{dose stop date} - \text{dose start date} + 1)}$			
# tablets per day: 1 tablet per day: 1mg, 2mg, 4mg, 6mg, 8mg, 10mg 2 tablets per day: 12mg, 16mg 3 tablets per day: 24mg			

 ○ darbepoetin alfa Every 4 Week Exposure Records: Based on Number of Doses Given 			
Duration of Exposure Record	Under Compliant	Compliant	Over Compliant
1 – 14 days	< 1 dose	1 dose	> 1 dose
15 – 42 days	< 1 dose	1 or 2 doses	> 2 doses
43 – 70 days	< 2 doses	2 or 3 doses	> 3 doses

CONFIDENTIAL

201410

Exposure and Compliance			
71 – 98 days	< 3 doses	3 or 4 doses	> 4 doses
99 – 126 days	< 4 doses	4 or 5 doses	> 5 doses
Etc.			
○ darbepoetin alfa Every 2 Week Exposure Records: Based on Number of Doses Given			
Duration of Exposure Record	Under Compliant	Compliant	Over Compliant
1 – 7 days	< 1 dose	1 dose	> 1 dose
8 – 21 days	< 1 dose	1 or 2 doses	> 2 doses
22 – 35 days	< 2 doses	2 or 3 doses	> 3 doses
36 – 49 days	< 3 doses	3 or 4 doses	> 4 doses
50 – 63 days	< 4 doses	4 or 5 doses	> 5 doses
64 – 77 days	< 5 doses	5 or 6 doses	> 6 doses
78 – 91 days	< 6 doses	6 or 7 doses	> 7 doses
92 – 105 days	< 7 doses	7 or 8 doses	> 8 doses
Etc.			
○ darbepoetin alfa Every Week Exposure Records: Based on Number of Doses Given			
Duration of Exposure Record	Under Compliant	Compliant	Over Compliant
1 – 3 days	< 1 dose	1 dose	> 1 dose
4 – 10 days	< 1 dose	1 or 2 doses	> 2 doses
11 days	< 1 dose	1 or 2 or 3 doses	> 3 doses
12 – 17 days	< 2 doses	2 or 3 doses	> 3 doses
18 days	< 2 doses	2 or 3 or 4 doses	> 4 doses
19 – 24 days	< 3 doses	3 or 4 doses	> 4 doses
25 days	< 3 doses	3 or 4 or 5 doses	> 5 doses
26 – 31 days	< 4 doses	4 or 5 doses	> 5 doses
32 days	< 4 doses	4 or 5 or 6 doses	> 6 doses
33 – 38 days	< 5 doses	5 or 6 doses	> 6 doses
39 days	< 5 doses	5 or 6 or 7 doses	> 7 doses
40 – 45 days	< 6 doses	6 or 7 doses	> 7 doses
46 days	< 6 doses	6 or 7 or 8 doses	> 8 doses
47 – 52 days	< 7 doses	7 or 8 doses	> 8 doses
53 days	< 7 doses	7 or 8 or 9 doses	> 9 doses
Etc.			

 • Compliance will be summarized for the following time periods: Day 1 - < Week 28, Week 28 - < Week 52, and Day 1 - < Week 52 (Overall compliance). • Within each period, the percentage of time that a subject spent in each of the 3 categories above or with missing compliance data will be determined. • A subject's compliance category will be the category that corresponds to the highest percentage of total time. In the unlikely event of a tie, the lower compliance category will be 			

Exposure and Compliance
chosen (i.e., in a tie between under and compliant, under is chosen; in a tie between compliant and over, compliant is chosen; and in a tie between under and over, under is chosen; in a tie with missing, missing is chosen).

10.6.3. Efficacy

10.6.3.1. Hemoglobin Endpoints

Hemoglobin Values
Central Laboratory and HemoCue Hgb Values

 When source of Hgb measurement is not specified: 
 For reporting purposes, central laboratory Hgb values will be used, unless otherwise specified. However, if a central laboratory Hgb value is missing, a corresponding non-missing HemoCue Hgb value will be used. This approach will be used for the primary Hgb analysis. Some displays may be created for either central laboratory Hgb values only or HemoCue Hgb values only. The central laboratory summary will be considered the primary summary in this case.
Evaluable Hemoglobin Values

 Evaluable Hgb values are on-treatment Hgb values (see Section 10.4.1.1) that are not taken within the 8 weeks following a red blood cell transfusion, a whole blood transfusion, or a non-randomized ESA treatment which occurs on or after the randomization date. Red blood cell transfusions, whole blood transfusions and non-randomized ESA treatments occurring on or after the randomization date are identified by comparing the start and stop date of the respective transfusion or ESA concomitant medication record to the randomization date.
Imputed Hemoglobin Values

 For each missing value between baseline to Week 52 (inclusive), 200 imputed values will be generated using the multiple imputation method (see Section 7.1.2). The average of these 200 imputed values will be used as the value for this missing value in the summary tables and figures. For the primary efficacy Hgb analysis and the corresponding subgroup analyses using all available observed and imputed Hgb values (on and off-treatment), Rubin's rules [Rubin, 1987] will be used to combine results of the imputed datasets using SAS PROC MIANALYZE procedure.
EP Hemoglobin Value for Primary Hgb Analysis

 For each subject, the mean of all available (on and off treatment) Hgb values during the EP (See Section 10.6.1) including any imputed and unscheduled Hgb values that were taken during this time period. Should the assessment dates for Hgb values from the Early Treatment Discontinuation visit fall within the EP, then these values will be included as unscheduled Hgb values. Hgb values from the Follow-up visit will not be included in the EP mean.

CONFIDENTIAL

201410

Hemoglobin Values					
EP Hemoglobin Value for While On-Treatment Evaluable Hgb Supportive Analysis					

 For each subject, the mean of all evaluable Hgb values during the EP (See Section 10.6.1) including any evaluable unscheduled Hgb values that were taken during this time period. Should the assessment dates for Hgb values from the Early Treatment Discontinuation visit fall within the EP, then these values will be included as unscheduled Hgb values. Hgb values from the Follow-up visit will not be included in the EP mean. 					
EP Hemoglobin Value for Alternative EP Supportive Analyses					

 For each subject, the mean of all Hgb values during the Alt. EP (See Section 10.6.1) including any imputed and unscheduled Hgb values that were taken during this time period. This analysis will be conducted using all available (on and off treatment) Hgb values and separately using evaluable Hgb values only. Should the assessment dates for Hgb values from the Early Treatment Discontinuation visit fall within the Alt. EP, then these values will be included as unscheduled Hgb values. Hgb values from the Follow-up visit will not be included in the Alt. EP mean. 					
Use of Unscheduled Hemoglobin Values and Multiple Hgb Values on the Same Date					

 The scenarios outlined below provide guidance on the use of unscheduled Hgb values and multiple Hgb values occurring on the same date. Each row represents a single calendar date. Rows outlining scenarios where there is at least one central lab Hgb and at least one HemoCue Hgb on the same date apply only for the derivation of Hgb values to be used in the primary Hgb analysis, where central lab values are used if they are available and if the central lab value is missing, then a corresponding non-missing HemoCue Hgb value is used. Rows outlining scenarios involving combinations of scheduled and unscheduled Hgb values of the same type apply to all Hgb summaries and analysis. 					
Scheduled Central Lab Hgb Value	Unscheduled Central Lab Hgb Value	Scheduled HemoCue Hgb Value	Unscheduled HemoCue Hgb Value	Value to Use	Type/Label
x				Scheduled central lab Hgb value	Scheduled visit
	x			Unscheduled central lab Hgb value	Unscheduled
		x		Scheduled HemoCue Hgb value	Scheduled visit
		multiple ¹		Average of scheduled HemoCue Hgb values	Scheduled visit
			x	Unscheduled HemoCue Hgb value	Unscheduled
	multiple			Average of unscheduled central lab Hgb values	Unscheduled
			multiple	Average of unscheduled HemoCue Hgb values	Unscheduled
x	x			Average of central lab Hgb values	Scheduled visit
x		x		Scheduled central lab Hgb value	Scheduled visit
x			x	Scheduled central lab Hgb value	Scheduled visit
	x	x		Unscheduled central lab Hgb value	Unscheduled

CONFIDENTIAL

201410

Hemoglobin Values					
	x		x	Unscheduled central lab Hgb value	Unscheduled
		x	x	Average of HemoCue Hgb values	Scheduled visit
1: The dose adjustment algorithm will require sites to obtain two HemoCue Hgb values at some visits.					
Time In Range					
Time in Range During the EP					

 Number of days that a subject's evaluable Hgb is within the analysis range of 10-11.5 g/dL inclusive during the EP (See Section 10.6.1), including any unscheduled evaluable Hgb values that were taken during this time period. Use of unscheduled Hgb values follows the scenarios for unscheduled and multiple Hgb values. Linear interpolation is used to estimate Hgb between visits, accounting for any intermittent missing values (Rosendaal, 1993). 					
Percent Time in Range During the EP					

 Time in Range During the EP / [Earlier of (Date of the last evaluable Hgb value, Week 52 visit date) – Later of (Date of the first evaluable Hgb value that between Week 16 and Week 52 inclusive, Week 28 visit date)] Note: Percent time in/below/above range during the EP is only defined for subjects with a Treatment Stop Date that is on or after their Week 28 visit date, and have at least two evaluable Hgb values on different days, where at least one evaluable Hgb value is contained within the EP and another evaluable Hgb value occurs within the range of the Week 16 visit through 4 weeks following the Week 52 visit, inclusive. 					

